3.3 Primary Effectiveness Endpoint

The primary effectiveness endpoint (PEE) is the proportion of Treatment Subjects with Treatment Success through the Day 360 Assessment. Treatment Success is defined as Persistent AF Acute Procedural Success AND Persistent AF Chronic Success.

3.3.1 Persistent AF Acute Procedural Success

Persistent AF Acute Procedural Success is defined as:

- The isolation of all attempted PVs as clinically assessed at the end of the procedure by entrance block performed with or without adenosine testing, AND
- The isolation of the left atrial PW as clinically assessed at the end of the procedure, performed with or without adenosine testing, via interrogation by multipolar diagnostic catheter or 3D electroanatomical mapping

Both PWI and PVI must be achieved using only the FARAWAVE Catheter to be classified as a Persistent AF Acute Procedural Success. If the Investigator determined that subject welfare required intervention for an accessory pathway, AVNRT or spontaneously occurring treatment-emergent AFL or AT, ablation for these arrhythmias may be performed using any commercially available RF ablation catheter, and these permitted ablations do not constitute Persistent AF Acute Procedural Failure.

3.3.2 Persistent AF Chronic Success

Persistent AF Chronic Success is defined as freedom from any of the following through the Day 360 Assessment after the Blanking Period, excluding documented CTI-dependent AFL²:

- a. **Arrhythmia:** Occurrence of any Detectable AF, AFL or AT
- b. **Re-ablation:** Any re-ablation for AF, AFL or AT
- c. **Cardioversion:** Any electrical cardioversion for AF, AFL or AT
- d. **AAD Use:** Use of a Non-Failed Class I / III AAD or amiodarone

Within the Blanking Period, recurrent arrhythmias can be managed with AADs, cardioversion or one re-ablation procedure with the FARAPULSE PFA System without constituting Persistent AF Chronic Failure. Titration of Class I/III antiarrhythmic medications are allowed during the Blanking Period. Subjects are allowed to remain on Class I/III antiarrhythmic medications at the historic maximum ineffective dose (prior to the ablation procedure) after the 90-day Blanking Period, except amiodarone. Subjects that undergo more than one re-ablation procedure within the Blanking Period will be classified as a Persistent AF Chronic Failure. Complete definitions of the endpoint terms (including Blanking Period, Detectable AF, AFL, or AT, Failed AAD and Non-Failed AAD), can be found in **Section 23.2**.

3.4 Additional Endpoints and Assessments

The following additional endpoints and assessments will be analyzed and reported for the ADVANTAGE AF Study.

3.4.1 Additional Safety Endpoints

The following endpoints will be descriptively analyzed through the Day 360 Assessment in Treatment Subjects and the Day 30 Assessment in Attempt Subjects:

- **Composite Non-Serious Adverse Events:**
Defined as the proportion of subjects with one or more composite nonserious AEs otherwise as defined in **Table 3.2-2: Composite Serious Adverse Event Definitions**.
- **Related Adverse Events**
Defined as the proportion of subjects with one or more device or procedure-related AEs
- **Any Serious Adverse Event**
Defined as the proportion of subjects with one or more SAEs whether or not device or procedure-related
- **Post-Blanking Arrhythmia Hospitalizations**
Defined as the proportion of Treatment subjects with one or more physician-directed admission to an inpatient hospital facility for at least two consecutive calendar days for the primary purpose of diagnosing or treating AF, AFL or AT beginning after Day 90
- **Post-Blanking Cardioversions**
Defined as the proportion of Treatment subjects with one or more electrical cardioversions for AF, AFL or AT after Day 90

3.4.2 Additional Effectiveness Endpoints

The following endpoints will be descriptively analyzed in Treatment Subjects at the indicated time points:

² Post-blanking CTI-dependent AFL or re-ablation or cardioversion for CTI-dependent AFL does not constitute Treatment Failure.

- **Persistent AF Acute Procedural Success**
Defined in **Section 3.3.1** at the conclusion of the Index Procedure / Rescheduled Index Procedure
- **Persistent AF Chronic Success**
Defined in **Section 3.3.2** through the Day 360 assessment
- **Single Procedure Treatment Success**
Treatment Success as defined in **Section 3.3.1** but counting subjects with any re-ablation for AT, AFL, or AT as Treatment Failures
- **Off Drug Treatment Success**
Treatment Success as defined in **Section 3.3.1** but counting subjects treated with any Class I / III AAD after Day 90 as Treatment Failures
- **Re-Ablation Rate**
Defined as the proportion of subjects who receive one or more re-ablations during study follow-up for AF, AFL, or AT, at any time during follow-up, and subdivided by re-ablation during Days 0 – 90 and by Days 91 and thereafter.

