Persistent atrial fibrillation	PersAF is defined as continuous AF that is sustained beyond 7 days, but not greater than 12 months duration.
Pulmonary vein dimensions	
For the purpose of assessing potential PV stenosis:
 
 • PV dimensions will be measured in two roughly orthogonal diameters approximating the longest and shortest diameters at the plane of measurement. • The measured PV diameter is defined as the geometric mean of these 2 measurements. • The PV cross-sectional area is computed using the formula for area of an ellipse, where the longest and shortest axis measurements of the PV diameter serve as the major and minor axes of the ellipse, using half of each axis diameter as the radii for calculation.
Roll-In Subjects	Roll-In Subjects are defined in Section 4.2.1 , Section 4.3 and Section 6.6.2 .
Severe COVID-19 Subjects	
Any study subject who contracts COVID-19 infection during study participation that:
 
 • Requires supplemental oxygen, positive pressure ventilation, and / or intubation OR • Is associated with any medically serious sequelae of COVID 19, including but not limited to new onset cardiac arrhythmia, heart failure, myocarditis, neurologic dysfunction or other organ dysfunction, or thromboembolic disease. 
Such subjects will be initially defined by the Investigator and confirmed by the CEC. The Onset Date will be the date of symptom onset in a subsequently clinically confirmed case of COVID-19 infection.

Source data Ref: ISO 14155	All information in original records, certified copies of original records of clinical findings, observations, or other activities in a clinical investigation, necessary for the reconstruction and evaluation of the clinical investigation. This includes source data initially recorded in an electronic format.
Source document Ref: ISO 14155	Original or certified copy of printed, optical, or electronic document containing source data, including TSFs.
Treatment Failure	Treatment Failure is the absence of Treatment Success due to one or more protocol-stipulated reasons.
Treatment Subjects	Treatment Subjects are defined in Section 6.6.5 .
Treatment Success	Treatment Success is defined in Section 3.3 .

Term	Definition

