Treatment Success as defined in **Section 3.4** but counting subjects with any re-ablation for AF, AFL, or AT as Treatment Failures

- **Off Drug Treatment Success**

Treatment Success as defined in **Section 3.4** but counting subjects treated with any Class I / III AAD after Day 90 as Treatment Failures

- **Re-Ablation Rate**

Defined as the proportion of subjects who receive one or more re-ablations during study follow-up for AF, AFL, or AT, at any time during follow-up, and subdivided by re-ablation during Days 0 – 90 and by Days 91 and thereafter. CTI only re-ablation is excluded for subjects who did not receive CTI ablation with the FARAPPOINT catheter.

- **AF, AFL, and AT Burden**

Descriptive statistics on AF, AFL, and AT burden, as defined in Section 23.2 and assessed during the observation period from Day 91 to Day 360 Assessment. AF, AFL, and AT burden will also be calculated for the days from LUX-Dx activation to the Index/ Rescheduled Index Procedure (up to 30 days pre-procedure) and compared to the burden calculated from Day 91 to Day 360 Assessment. Additionally, AF, AFL, and AT burden statistics from Day 91 to Day 360

will be stratified by recurrence based on LUX-Dx detected AF, AFL, or AT using various episode duration thresholds.

- **Healthcare Utilization by AF, AFL, and AT Burden**

Healthcare utilization, defined by outcomes of all-cause hospitalization, cardioversion for AF, AFL, or AT recurrence outside of an ablation procedure, re-ablation for AF, AFL, or AT and unscheduled cardiovascular follow-up assessments, will be compared between subjects grouped by AF, AFL, and AT burden from Day 91 to Day 360 Assessment. Burden groups will include rates of 0%, 0-0.1%, 0.1-1%, 1-5%, 5-10%, and >10% AF, AFL, and AT burden.

- **Healthcare Utilization by AF, AFL, or AT Recurrence Duration**

Healthcare utilization, defined by outcomes of all-cause hospitalization, cardioversion for AF, AFL, or AT recurrence outside of an ablation procedure, re-ablation for AF, AFL, or AT and unscheduled cardiovascular follow-up assessments will be compared between subjects grouped by longest duration of AF, AFL, or AT captured by LUX-Dx (based on continuous monitoring) between Day 91 and Day 360 Assessment. Groups will include no recurrence and longest duration of 0-6 minutes, 6 minutes – 1 hour, 1-6 hours, 6-24 hours, and \geq 24 hours.

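### Phase 1 Section 3.4.2 bases Single Procedure and Off Drug Treatment Success on the acute-isolation section, and the Single Procedure re-ablation list omits AF

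*Combined protocol and SAP*

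**What the plan says.** Phase 1 Section 3.4.2 lists five additional effectiveness endpoints for descriptive analysis in Treatment Subjects. Two are built on Treatment Success with one extra failure rule each.

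- Single Procedure Treatment Success starts from Section 3.3.1 and adds a re-ablation rule: "but counting subjects with any re-ablation for AT, AFL, or AT as Treatment Failures".
- Off Drug Treatment Success reads: "Treatment Success as defined in Section 3.3.1 but counting subjects treated with any Class I / III AAD after Day 90 as Treatment Failures".

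Section 3.3.1 opens with "Persistent AF Acute Procedural Success is defined as" and has two elements. One concerns the veins: "The isolation of all attempted PVs as clinically assessed at the end of the procedure by entrance block performed with or without adenosine testing". The other sets a matching requirement for the posterior wall: "The isolation of the left atrial PW as clinically assessed at the end of the procedure". It contains nothing about follow-up.

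The composite is defined one level up, in Section 3.3: "Treatment Success is defined as Persistent AF Acute Procedural Success AND Persistent AF Chronic Success". The definitions table agrees: "Treatment Success is defined in Section 3.3".

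In Appendix A Section 3.5.2, the Phase 2 versions of both endpoints cite the parent section (there 3.4), and the Single Procedure rule reads "but counting subjects with any re-ablation for AF, AFL, or AT as Treatment Failures".

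**The concern.** Section 8.1.3 says the additional effectiveness endpoints are analysed as the referenced section defines them, and it refers to Section 3.4.2. No other Phase 1 section defines these two endpoints, so the wording of 3.4.2 is the operative rule.

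Two separate defects follow. The reference drops the whole chronic component from both endpoints: recurrence, cardioversion, re-ablation after blanking, and use of a Non-Failed AAD or amiodarone. The repeated AT removes AF, the arrhythmia under study, from the list of re-ablations that fail Single Procedure success.

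Table 3.5-1 calls both endpoints important clinical measures for physicians. What is at stake is whether the figures reported under these names mean what a reader would take them to mean.

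**Working it through.** This is mainly a check of text and cross-references. The plan gives no figure for either endpoint, so there is none to reproduce.

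**Step 1: what each definition counts as success.**

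| Version | Single Procedure | Off Drug |
|---|---|---|
| As written | Acute isolation and no re-ablation for AFL or AT | Acute isolation and no Class I / III AAD after Day 90 |
| Reference corrected only | Acute and chronic success, and no re-ablation for AFL or AT | Acute and chronic success, and no Class I / III AAD after Day 90 |
| List corrected only | Acute isolation and no re-ablation for AF, AFL or AT | As written (the list does not apply) |
| Both corrected | Acute and chronic success, and no re-ablation for AF, AFL or AT | Acute and chronic success, and no Class I / III AAD after Day 90 |

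The as-written row contains no recurrence component. Recurrence through Day 360 appears only in Section 3.3.2. Off Drug has the reference error alone. Single Procedure has both errors, and correcting one leaves it wrong.

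**Step 2: what the missing AF does once the reference is corrected.**

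- Re-ablation for AF after the Blanking Period already fails under Section 3.3.2.
- A second re-ablation within the Blanking Period also fails under Section 3.3.2.
- A first re-ablation within the Blanking Period does not fail (Sections 3.3.2 and 7.13.1).

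The third case is the main one that Single Procedure success adds to the primary endpoint. With AF absent from the list, a subject re-ablated for AF in that window remains a success unless Section 3.3.2 fails the subject on another ground.

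**Step 3: size of that remaining error.** Inputs are 258 planned Treatment Subjects (Section 4.2.1) and the planned 55% success rate (Table 8.1-4). The documents give no blanking-period re-ablation rate, so 3-6% is assumed.

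- Subjects with a first blanking-period re-ablation for AF: 0.03 × 258 = 7.7 to 0.06 × 258 = 15.5, or about 8-15. This is a ceiling, reached only if all of them are otherwise successes.
- If they otherwise succeed at 55%: 0.55 × 7.7 = 4.3 to 0.55 × 15.5 = 8.5, or about 4-9.
- As a share of 258: at most 3-6 percentage points, or 0.55 × 3 = 1.65 to 0.55 × 6 = 3.3 points under the 55% assumption.

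**The case against.** The best reply is that nobody would be misled. Treatment Success is a capitalised, defined term, and Section 3.3 and Table 23.2-1 both give its meaning. Section 3.3.1 defines a differently named quantity, which Section 3.4.2 already lists as an endpoint of its own. A rule about drugs after Day 90 does not fit an end-of-procedure measure. The Re-Ablation Rate in the same list names AF, AFL, or AT. It is also reported separately for Days 0-90 and from Day 91, so early re-ablations are disclosed anyway. The operative programming may already be right: Sections 8.3.2 and 8.3.6 refer to a separate SAP whose Phase 1 text was not available for this check.

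Most of this stands as evidence of intent. It does not make the text correct. Appendix A does not govern Phase 1, because its Section 4.1.1 keeps Phase 1 subjects under the protocol version in which they enrolled. Section 8.3.6 asks that changes to planned analyses be documented, so the intended definition should be written down and not silently applied.

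A reader might also infer more than the documents support:

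- **That the reported figures would be overstated by 40 points or more.** That subtracts the planned 55% from an assumed acute rate of 95-100%, and the plan sets no expected acute rate for this trial. Against the plan's own meta-analytic 67.23% the gap would be about 28-33 points. Either subtraction ignores the failures the literal text retains: any Class I / III AAD after Day 90 for Off Drug, and AFL or AT re-ablation for Single Procedure.
- **That every blanking-period AF re-ablation would score as a success once the reference is corrected.** Section 3.3.2 can still fail those subjects on other grounds.
- **That these words are what makes Phase 1 and Phase 2 differ.** The phases also differ in recurrence monitoring, analysis set and handling of CTI-dependent flutter. The correction removes none of those differences.

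**Conclusion.** The point holds as a drafting error in two endpoint definitions: wrong as written, minor in severity. Taken literally, neither endpoint counts arrhythmia recurrence through Day 360. With the reference alone corrected, Single Procedure success would still miss the main case that it adds to the primary endpoint.

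The defect itself needs no assumption. Its size does: the upper bound of 8-15 subjects rests on the assumed 3-6% rate, and the figure of about 4-9 also assumes that re-ablated subjects otherwise succeed at 55%. No numerical error in reported results is claimed for the wrong reference, since that would depend on an acute rate and drug-use pattern the plan does not give and on SAP text not seen here.

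Both endpoints are descriptive and the study has no secondary endpoints. The primary endpoints, sample size, power, type I error and study-success rule are unaffected.

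**What to change.** In Phase 1 Section 3.4.2:

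1. Change the reference in Single Procedure Treatment Success from Section 3.3.1 to Section 3.3.
2. Make the same change in Off Drug Treatment Success.
3. In the Single Procedure rule, change AT, AFL, or AT to AF, AFL, or AT.

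This aligns the text with Appendix A Section 3.5.2. Make the Phase 1 SAP match. If the analyses have already been run, state in the clinical study report which definitions were used.

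The cost is three word-level edits, with no new data, subjects or analyses. Single Procedure success may come out slightly lower than it would with only the reference corrected.

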3.4.3 Procedural Assessments

The following assessments will be descriptively analyzed at the completion of the Index Procedure / Rescheduled Index Procedure:

Assessments of procedure durations (recorded and rounded to the nearest minute)

- **Procedure Time**
Defined as the recorded time of initiation of venous access to the recorded time of venous access closure completion
- **LA Dwell Time**
Defined as the recorded time between the insertion of the first device into the LA and the removal of the last device from the LA
- **PVI and PWI Ablation Time**
Defined as the recorded time from the first FARAWAVE PFA Catheter application to the last FARAWAVE PFA Catheter application.
- **Fluoroscopy Time**
Defined as the recorded total duration of exposure to fluoroscopic imaging

Characterization of lesion sets

- **PVI Ablations**
Defined as the number of applications in each attempted vein
- **PWI Ablations**
Defined as the number of applications during ablation of the LA posterior wall
- **CTI Ablations**
Defined as the number of applications during CTI ablation
- **Other Ablations**
For subjects undergoing welfare-required ablations for an accessory pathway, AVNRT, left-sided AFL or incessant AT a listing and descriptive summary of ablation lesions delivered.

3.4.4 Quality of Life Assessments

The following assessments will be descriptively analyzed between Baseline and Day 180, and between Baseline and Day 360.

- The 3-level EuroQol standardized questionnaire of health states (EQ-5D-3L)

- The Atrial Fibrillation Effect on Quality of Life (AFEQT) instrument for the measurement of health-related quality of life

3.5 Summary of Study Endpoints

Each of the ADVANTAGE AF Study endpoints corresponds to one or more specific objectives which are listed and justified in the following table.

Table 3.5-1: Primary Endpoint Objectives and Justification

OBJECTIVES	ENDPOINTS	JUSTIFICATION
Primary		
Establish the safety of the FARAPULSE PFA System	Composite of 7-day, 30-day, and Day 360 study-specific CSAEs as defined in Section 3.2	Composite list of CSAEs includes those AEs typically associated with catheter ablation of AF, consistent with other IDE Trial definitions. Performance goal and expected rates calculated from a meta-analysis of controlled and IDE clinical studies on PersAF ablation
Establish the effectiveness of the FARAPULSE PFA System	Treatment Success through 360 days as defined in Section 3.3	Definition of Treatment Success is consistent with from other IDE Trial definitions. Performance goal and expected rates calculated from a meta-analysis of controlled and IDE clinical studies on PersAF ablation.
Secondary		
There are no secondary endpoints for the ADVANTAGE AF Study.		
Additional		
Safety characterization	Composite non-serious adverse events	It is useful to demonstrate a more generalized safety profile
Safety characterization	Device or procedure-related adverse events	It is useful to demonstrate a more generalized safety profile
Safety characterization	Any SAE	It is useful to demonstrate a more generalized safety profile
Safety and economic impact demonstration	Post-blanking hospitalizations for AF, AFL, or AT	An important patient and economic impact

OBJECTIVES	ENDPOINTS	JUSTIFICATION
Safety and economic impact demonstration	Post-blanking electrical cardioversions for AF, AFL, or AT	An important patient and economic impact
Demonstrate acute effectiveness	Acute Procedural Success	Component of primary effectiveness endpoint
Demonstrate chronic effectiveness	Chronic Success	Component of primary effectiveness endpoint
Demonstrate single procedure effectiveness	Single Procedure Treatment Success	Important clinical measure for physicians
Demonstrate off-drug effectiveness	Off Drug Treatment Success	Important clinical measure for physicians
Report the rate of repeat procedures	Re-ablation rate	Important clinical measure for physicians
Report key procedural durations	Assessments of procedure durations (procedure, LA dwell, PVI / PWI ablation, and fluoroscopy times)	Important procedural parameters for physicians
Characterize ablative intervention	Characterization of lesion sets (PVI, PWI, CTI and Other)	Important procedural parameter for physicians
Characterize change in subjects' self-reported health status	The EuroQol (EQ-5D-3L) and AFEQT instruments	Important patient reported outcome measures for health status changes

4 Study Design

[figure not shown]
4.1 Overview of the ADVANTAGE AF Study Design

The ADVANTAGE AF Study is a prospective, single arm, open label, multi-center IDE pivotal study utilizing the FARAPULSE PFA System in the treatment of patients with PersAF.

Subjects requiring ablative intervention for PersAF meeting study entry criteria will undergo percutaneous ablative pulmonary vein isolation (PVI) and left atrial posterior wall isolation (PWI) using the FARAWAVE PFA Catheter. Subjects meeting protocol criteria will undergo ablative interruption of the cavo-tricuspid isthmus (CTI) using a commercially available BSC RF catheter.

Subjects will be followed at Pre-Discharge, Day 7, Day 30, Day 90, Day 180, and Day 360. The Blanking Period will include Days 0 through 90, after which subjects will be monitored twice per month plus symptom-driven event monitoring, as well as Day 180 and Day 360 24-hour Holter monitoring.

Figure 4.1-1: ADVANTAGE AF Study Design

4.2 Scale and Duration

4.2.1 Number of Subjects

Approximately 417 treated subjects will be enrolled in this study (up to 159 Roll-In Subjects and approximately 258 Treatment Subjects).

Roll-In Subjects (up to 159): The first subject enrolled by each ablating Investigator at each site will be treated with the investigational device(s) as part of Investigator preparation, up to a maximum of 159 subjects across 53 investigational sites. Roll-In procedures may be adapted based on prior experience, or additional subjects may be required as described in **Section 4.3**.

Treatment Subjects (258): A planned 258 Treatment Subjects will be enrolled to support the proposed primary study outcomes. No site may enroll more than 33 Treatment Subjects(13% of those planned). Subject enrollment will stop once approximately 258 Treatment Subjects are accrued.

